Subjects will receive 160 mg Micardis brand telmisartan (Boehringer-Ingelheim) in the form of two 80 mg pills, taken together, once daily, starting 2 days prior to HCT (day -2). All subjects will receive telmisartan in addition to the standard GvHD prophylaxis and treatment regimens prescribed by their transplant physician (see section 5.3.5). Systolic and Diastolic Blood pressure will be monitored at least every 4 hours while in the hospital. Patients who develop severe hypotension (\geq grade 3) will have their doses adjusted accordingly (see section 5.3.4 for dose modification schedule). Once the patient is discharged post-HCT, treatment will continue in the outpatient setting. Treatment will continue through Day +98 post-HCT for a total of 104 days (day -5 to day +98) in the first five enrollees, and 101 days (Day -2 to Day +98) in the subsequent subjects, assuming 160 mg is well tolerated in 4 or more of the first 5 subjects. After treatment

discontinuation on or before day +98 post-HCT, subjects will be followed for up to 6 months (Day +180) for primary and secondary endpoints.

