5.2 Study Endpoints

5.2.1 Efficacy Endpoints

- Grade II GVHD as per 1994 Consensus Conference on Acute GVHD Grading criteria [104]
- Grade III-IV GVHD as per 1994 Consensus Conference on Acute GVHD Grading

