8.3 Statistical Analysis Plan

8.3.1 Efficacy Endpoints for Grade III-IV and Grade II GVHD.

The statistical test used for endpoints (Z test of proportions) takes the currently available 3 year JTCC data as the historical control data set for comparison. In reviewing these data, as currently available, it appears that the JTCC rates of severe GVHD, NRM, and cancer relapse are somewhat lower (i.e. better patient outcomes) than the national averages from published studies. For our final determinations of significance, we will use updated JTCC 3 year data as they become available at time of study completion.

Outcome variables examined include engraftment, GVHD, relapse, and NRM, however the efficacy hypotheses are constructed in relation to GVHD only.

Primary endpoint analysis

Historic GVHD data are available on 178 allogeneic transplants, of whom 46 (26%) experienced grade III or IV acute GVHD. All the other allogeneic transplantees (74%) had grade II GVHD. Based on these data, if 8 or fewer of the total 60 study participants experience grade III - IV acute GVHD during the course of the study, we will have demonstrated a protective effect for this criterion, with a $p < 0.05$, based on a one-way Z test for a decreased proportion.

Sample Size and Power Calculation Considerations

If we use the proportion $P=0.26$ as the rate of Grade III - IV GVHD in the current standard treatment, then using a one-sided exact test of the proportion and significance level of 0.05, testing if 9/60 (15%) rate of Grade III-IV GVHD is achievable with telmisartan treatment will have 58.8% power to detect this effect, if it exists. Testing for a 12% rate would achieve 82.2% power. Using the recommended level of significance, 0.025, for a one-sided test, testing if the grade III-IV GVHD by day 100 is 0.15, would have power of 44.4% of detecting this effect. At the 2.5 % level, testing if the rate is less than 0.11, will have 79.0 % power of detecting. Testing if the rate of grade III-IV in telmisartan treated transplantees is 0.10, will have 85.8% power of detecting this effect using the 2.5 % level of significance.

Numeric Results for testing $H_0: P = P_0$ versus $H_1: P < P_0$ using the PASS13 sample size software Test Statistic: Exact Test

Power	N	Proportion		Target Alpha	Actual Alpha	Beta	Reject H_0 If $R \leq$ This
		Given H_0 (P_0)	Given H_1 (P_1)				
0.8584	60	0.2600	0.1000	0.0250	0.0140	0.1416	8
0.7899	60	0.2600	0.1100	0.0250	0.0140	0.2101	8

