Incidence of Grade II GVHD

The historical data reported a rate of incidence of 74%. At 5% level of significance, a one-sided exact test of whether telmisartan can attain lower levels of 62% (37/60), would achieve 63.2 % power of detecting this if it is indeed efficacious. A lower incidence rate of 60% will be detected with 74.5% power.

Using the recommended level of significance, 0.025, a one-sided exact test of whether Telmisartan can attain the lower incidence rate of 62% will achieve a power of 52.8% to detect this effect. A one-sided exact test of whether the grade II GVHD incidence rate of 0.50 (30/60) can be attained by Telmisartan will have 97.4% power to detect this effect. A one-sided exact test of whether the incidence rate of 60% is possible with telmisartan will achieve power of 65.1% to detect it. A one-sided exact test of whether the grade II GVHD incidence rate of 0.57 can be attained by Telmisartan will have 80.5% power to detect this effect.

Numeric Results for testing $H_0: P = P_0$ versus $H_1: P < P_0$ using the PASS13 sample size software Test Statistic: Exact Test

Power	N	Proportion Given H0 (P0)	Proportion Given H1 (P1)	Target Alpha	Actual Alpha	Beta	Reject H0 if $R \leq$ This
0.9741	60	0.7400	0.5000	0.0250	0.0242	0.0259	37
0.8448	60	0.7400	0.5600	0.0250	0.0242	0.1552	37
0.8047	60	0.7400	0.5700	0.0250	0.0242	0.1953	37
0.7587	60	0.7400	0.5800	0.0250	0.0242	0.2413	37
0.6507	60	0.7400	0.6000	0.0250	0.0242	0.3493	37
0.5904	60	0.7400	0.6100	0.0250	0.0242	0.4096	37
0.5275	60	0.7400	0.6200	0.0250	0.0242	0.4725	37

Thus, with respect to grade 2 acute GVHD, if 37 or fewer patients of the 60 have grade 2 or lower acute GVHD, we will have demonstrated a drug effect at $p < 0.05$, using the one-way Z test of proportions.

To summarize, with only 26% of JTCC patients during the past 3 years exhibiting grade III or IV acute GVHD, we would have to see no more than 7 cases of grade III or IV acute GVHD (~ 12%) by the completion of the study to conclude that severe aGVHD had been reduced. However, with 74% of JTCC patients experiencing grade II aGVHD, we need only reduce that to 60%, or 36 of 60 patients having no more than grade II acute GVHD, in order to achieve significance.

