8.3.2 Analysis of Exploratory Data

For exploratory endpoint biomarkers other than microbiota 16S rRNA sequences, multivariate modification of cumulative incidence statistics of Fine and Gray will be used to evaluate the univariate and multiple effects of primary markers or secondary markers on endpoints. The cumulative incidence of primary endpoints of Grade III-IV GVHD at any time among all patients in the study will be based on the initial systemic diagnosis and treatment. Cox regression

analyses will be used to identify exploratory study parameters as risk factors for Grade III-IV GVHD. Exploratory assays with a P value $\leq .05$ for association with Grade III-IV GVHD in univariate testing will be entered in a multivariate Cox regression model.

Additionally, for each parameter, pairwise comparisons will be made between pre-transplant and each post-transplant time point. Statistical comparisons between GVHD(+) and GVHD(-) groups will be performed using a χ^2 or Fisher's exact test for categorical variables or the non-parametric Mann-Whitney U test for continuous variables. Mean values obtained from ELISA assays performed on pre- and post-transplant samples will be compared with the non-parametric Mann-Whitney U test for continuous variables. Next, the change in each blood factor at a given time relative to before the conditioning regimen was initiated will be compared using a paired t-test in GVHD (+) and GVHD (-) groups.

For 16S rRNA data, statistical analysis will follow the methods outlined above and detailed in Jenq et al. [99], briefly as follows:

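### Section 8.3.1 words the grade II success rule with the wrong event, rests it on a 74% null that leaves no historical patient at grade 0-I, and gives no test for the grade II-IV objective.

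*Combined protocol and SAP*

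**What the plan says.** The efficacy target is stated in several forms.

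- Sections 2.0, 3.1 and 6.3 name grade II-IV (in 3.1, grade II or greater).
- Section 5.2.1 lists two separate endpoints, "Grade II GVHD as per 1994 Consensus Conference on Acute GVHD Grading criteria" and "Grade III-IV GVHD as per 1994 Consensus Conference on Acute GVHD Grading", and no composite.
- Section 8.3.1 tests those two separately. Section 8.3.2 refers to "The cumulative incidence of primary endpoints of Grade III-IV GVHD at any time among all patients in the study".

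For the historical control, Section 8.3.1 reports 46 of 178 transplants (26%) with grade III-IV and then states: "All the other allogeneic transplantees (74%) had grade II GVHD". The final comparison is to be refreshed: "we will use updated JTCC 3 year data as they become available at time of study completion".

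The grade III-IV rule is success "if 8 or fewer of the total 60 study participants experience grade III - IV acute GVHD during the course of the study". The grade II rule is success "if 37 or fewer patients of the 60 have grade 2 or lower acute GVHD, we will have demonstrated a drug effect". The closing summary of 8.3.1 repeats it as 36 of 60 patients at grade II or below. The accompanying table tests H1: P < P0 with N = 60, P0 = 0.74 and rejection at 37 or fewer.

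On timing, the stopping rule for grade III-IV in Section 8.4 (Table 13) counts events by day 100, while Section 5.1 says "subjects will be followed for up to 6 months (Day +180) for primary and secondary endpoints".

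**The concern.** There are four linked problems.

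1. **Wording.** Both statements of the grade II rule put grade 0-I inside the event that must become rarer.
2. **Event.** Even as intended, a count of patients at exactly grade II falls whether they improve to 0-I or worsen to III-IV. It does not fall if III-IV is downgraded to II while an equal share of II moves to 0-I.
3. **Null.** The 74% is a complement. It implies a historical grade II-IV rate of 100%, although Section 5.3.5 gives guidelines for grade 0-I and Table 4 defines grade I. If some of the 132 were grade 0-I, the null is too high and an inert drug can pass.
4. **Objective.** Grade II-IV, the stated objective, has no null, cut-off or power. The 25% power claim in Section 8.2 covers grade II only.

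At stake is a declared drug effect on the wrong event or against the wrong reference rate.

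**Working it through.** **Inputs from the documents.** N = 60; 46/178 with grade III-IV; 178 − 46 = 132, and 132/178 = 0.742, used as P0 = 0.74; one-sided exact test at 0.025; cut-off 37; Table 13 boundaries.

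**Reproducing the plan.** With X ~ Binomial(60, p), P(X ≤ 37) is 0.0242 at p = 0.74 and 0.8047 at p = 0.57. Both match the table, so its arithmetic is sound.

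**The rule as worded.** At most 37 at grade 0-II means at least 60 − 37 = 23 at grade III-IV (38%); at most 36 means at least 24. The grade III-IV rule (8 or fewer) forces at least 60 − 8 = 52 at grade 0-II, so the two rules cannot both be met. Table 13 already stops at 21 of 60 if the events occur by day 100. The literal 37-rule is met with probability 0.024 if the true III-IV rate is 26%, below 0.00001 at 15%, 0.40 at 36% and 0.80 at 43%.

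**The intended rule on the plan's own split.** If trial patients follow the historical split, with nobody at grade 0-I, 37 or fewer at grade II is the same event as 23 or more at grade III-IV. The nominal 2.4% error then consists wholly of trials with more severe GVHD.

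**Inert drug when some of the 132 were grade 0-I.** The recoded counts are assumptions, because the documents give no split. Grade III-IV stays at 46/178, and P0 = 0.74 and cut-off 37 are held fixed. The joint probability comes from a patient-by-patient trinomial recursion with the Table 13 boundary applied after every patient. At a 26% III-IV rate this gives a crossing probability of 0.247, as in Table 14. At 46/178 the probability of not crossing is 0.760 in every row.

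| Recoded to 0-I | True grade II rate | P(≤ 37) | Met and no crossing | Met, given no crossing |
|---|---|---|---|---|
| 9 | 123/178 = 0.691 | 0.135 | 0.031 | 0.040 |
| 18 | 114/178 = 0.640 | 0.397 | 0.212 | 0.280 |
| 27 | 105/178 = 0.590 | 0.708 | 0.483 | 0.636 |
| 45 | 87/178 = 0.489 | 0.983 | 0.743 | 0.978 |

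**Benefit against harm.** Move 17 points out of grade II (74% to 57%).

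- To 0-I (benefit; III-IV 26%): P(≤ 37) = 0.805; met without crossing 0.566.
- To III-IV (harm; III-IV 43%): P(≤ 37) = 0.805; crossing 0.966; met without crossing 0.
- Harm with 10%, 20% or 30% of III-IV events after day 100 (assumed shares, not counted by Table 13): crossing 0.885, 0.716, 0.472; met without crossing 0.020, 0.138, 0.353.

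**Downgrading.** III-IV falls from 26% to 10%, those 16 points move into grade II, and 16 points of grade II move to 0-I. Grade II stays at 74%, so the grade II rule succeeds with probability 0.024. The separate III-IV test has power 0.858 here.

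**Grade II-IV.** The plan's own history gives (46 + 132)/178 = 100%, which is unusable as a null. For assumed nulls, with an exact one-sided 0.025 test, N = 60 and a 25% relative reduction:

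| Assumed II-IV null | Cut-off | Actual alpha | Power |
|---|---|---|---|
| 0.50 | 21 | 0.0137 | 0.399 |
| 0.60 | 27 | 0.0133 | 0.553 |
| 0.70 | 34 | 0.0196 | 0.781 |
| 0.80 | 41 | 0.0221 | 0.928 |

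**The case against.** The strongest reply is that nobody would apply the rule literally. The subsection heading, the direction of H1, the table and Section 8.2 all show that grade II incidence was meant. That is right, and it makes the first problem a correction of wording. It leaves the null, the ambiguity of an exactly-grade-II count and the missing II-IV test untouched.

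A second reply is that other safeguards would expose harm: Table 13, the other stopping rules, monthly DSMB review and the separate III-IV test, which would pass with probability below 0.000001 at a 43% III-IV rate. This holds for the harm case by day 100. It does not help in the inert-drug case, where III-IV is unchanged and Table 13 contains the false success only for the smallest recoding examined.

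The late-event shares are assumptions, and Section 2.0 treats the first 100 days as the acute period, so those figures carry little weight. The choice of 0.025 also matters: Section 8.3.1 declares success at p < 0.05 with a Z test. At exact one-sided 0.05 the assumed II-IV nulls would give cut-offs of 23, 29, 35 and 42 and power of 61%, 74%, 85% and 96%. I use 0.025 because the plan's tables do, and because that level yields its cut-offs of 37 and 8.

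The documents could instead be reconciled by changing 2.0, 3.1 and 6.3 to two endpoints, but the exactly-grade-II ambiguity would remain. Pilot status can excuse low power; it does not excuse a wrong event. The planned data update helps only if the grades are classified correctly, and nothing in the plan requires that check.

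**Conclusion.** The concern holds and must be fixed. Three parts need no assumption: the event is misworded twice, the historical split has 0 of 178 at grade 0-I, and the grade II-IV objective has no null, cut-off or power. The grade III-IV test runs in the right direction and its figures stand.

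The size of the error inflation depends on an unknown: how many of the 132 were grade 0-I. Over the assumed range of 9 to 45, an inert drug meets the grade II rule in 13% to 98% of trials, or 3% to 74% once Table 13 is taken into account. This presumes that the updated historical data repeat the same classification. The documents do not show whether any of the 132 are in fact mislabelled.

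**What to change.** - Reconcile Sections 2.0, 3.1, 5.2.1, 6.3 and 8.3.1. Define the event as grade II-IV acute GVHD over one stated window, for example day 100, which Section 8.4 and the power text of 8.3.1 already use. Keep grade III-IV as the separate test for severe GVHD.
- Obtain the 0-I / II / III-IV split of the 178 transplants over the same window. Verify or correct the statement that all the others had grade II, and apply the same check to the updated data.
- Re-derive one cut-off and its power with the exact one-sided 0.025 test already used in the tables.
- Replace both misworded statements of the success rule with the defined event.

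**Cost.** An amendment to 5.2.1 and 8.3.1, matching text in 2.0, 3.1 and 6.3, and a review of grades in the historical data. The documents do not say whether grade 0-I was recorded, so chart review of up to 132 transplants may be needed. The restated power may be less favourable: about 40% for a 25% relative reduction if the II-IV null were 0.50.

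### Section 8.3.1 sets two different success limits for grade III-IV GVHD, 8 or fewer and no more than 7 of 60, from the same 26% historical rate

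*Combined protocol and SAP*

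**What the plan says.** All of this is in section 8.3.1 of the combined protocol and SAP.

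- **Primary endpoint analysis.** The historical control is 46 of 178 transplants (26%) with grade III-IV GVHD. A protective effect is declared "if 8 or fewer of the total 60 study participants experience grade III - IV acute GVHD during the course of the study", at p < 0.05, "based on a one-way Z test for a decreased proportion".
- **Sample Size and Power Calculation Considerations.** The text first gives powers for a one-sided exact test at 0.05, including "Testing for a 12% rate would achieve 82.2% power". It then changes level: "Using the recommended level of significance, 0.025, for a one-sided test". The exact-test table that follows (N = 60, null rate 0.26, target alpha 0.025) rejects at 8 or fewer, with actual alpha 0.0140 and power 0.8584 at a true rate of 10% and 0.7899 at 11%.
- **Closing summary, under Incidence of Grade II GVHD.** Starting again from 26% ("with only 26% of JTCC patients during the past 3 years exhibiting grade III or IV acute GVHD"), it states: "we would have to see no more than 7 cases of grade III or IV acute GVHD (~ 12"%) in order to conclude that severe GVHD was reduced.
- **Opening paragraph.** For final significance, "we will use updated JTCC 3 year data as they become available at time of study completion".

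For grade II, the exact-test table rejects at 37 or fewer. The sentence below it reads "if 37 or fewer patients of the 60 have grade 2 or lower acute GVHD", and the summary mentions a reduction to 60%, or 36 of 60.

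**The concern.** The number of patients, the endpoint and the historical rate are the same in both places, but the largest count that still means success is 8 in one and 7 in the other. The summary's wording states a requirement, not an illustration. Nothing says which sentence governs.

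The study is open-label and single-arm, so the count accumulates in view of the investigators. If it ends at 8, the plan supports either conclusion, and the choice would be made with the result known. The design power depends on the same choice. A reader also cannot settle it from the surrounding text, which moves between a Z test and an exact test and between 0.05 and 0.025.

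**Working it through.** **Inputs.** n = 60; null rate P0 = 0.26, from 46/178 = 0.258 (Primary endpoint analysis); true rates 10%, 11%, 12% and 15%, the ones used in the power text and table. X is the number of grade III-IV cases, binomial with n = 60.

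**Step 1: reproduce the plan's table.** With the limit at 8, P(X ≤ 8 | 0.26) = 0.0140, P(X ≤ 8 | 0.10) = 0.8584 and P(X ≤ 8 | 0.11) = 0.7899. All three match.

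**Step 2: exact size and power for each candidate limit.**

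| Limit | Exact alpha at 0.26 | Power at 10% | Power at 11% | Power at 12% |
|---|---|---|---|---|
| ≤ 7 | 0.0055 | 75.2% | 66.2% | 56.7% |
| ≤ 8 | 0.0140 | 85.8% | 79.0% | 71.0% |
| ≤ 9 | 0.0312 | 92.7% | 88.1% | 82.2% |
| ≤ 10 | 0.0620 | 96.6% | 93.9% | 90.1% |

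The exact-test limit is 8 at one-sided 0.025 and 9 at one-sided 0.05. Neither level gives 7.

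**Step 3: where the quoted power belongs.** The 82.2% at a 12% rate is P(X ≤ 9 | 0.12) = 0.8224. The 58.8% quoted at 15% is likewise P(X ≤ 9 | 0.15) = 0.5877. Both are correct for an exact test at 0.05. The 9/60 in that text is a target rate, and no decision sentence sets the limit at 9.

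**Step 4: does 8 cases pass the named test?** The decision sentence names a one-sided Z test at p < 0.05 without giving its form. The observed proportion is 8/60 = 0.1333. Writing p for this proportion, the one-sample form is z = (0.1333 − 0.26) / √(0.26 × 0.74 / 60) = −2.24. One-sided p-values for 8 cases:

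| Form | Uncorrected | Continuity-corrected |
|---|---|---|
| One-sample, null variance | 0.0126 | 0.0183 |
| One-sample, observed variance | 0.0019 | 0.0035 |
| Two-sample against 46/178, pooled | 0.0227 | 0.0342 |
| Two-sample against 46/178, unpooled | 0.0112 | 0.0188 |

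All eight are below 0.05. Across these forms the limit at 0.05 runs from 8 to 10 and is never 7.

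**Step 5: how often the conflict decides the trial.** It bites only at X = 8. P(X = 8) = 0.1068, 0.1281 and 0.1427 at true rates of 10%, 11% and 12%, and 0.0085 at 0.26.

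**Step 6: effect of updating the historical data.** Assume, for illustration, that the denominator stays at 178 and the exact test at one-sided 0.025 is used. Then 43 historical events give a limit of 7, 44 to 47 give 8, and 48 give 9.

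**Step 7: grade II.** A count of 36 satisfies a limit of 37, so those two numbers can coexist. The counted event is the obstacle. The decision sentence counts patients at grade 2 or lower. With at most 8 grade III-IV cases, at least 60 − 8 = 52 patients are at grade II or lower, and 52 exceeds 37. Conversely, 37 or fewer at grade II or lower means at least 60 − 37 = 23 grade III-IV cases.

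**The case against.** **The fixed counts are provisional.** Final significance is to be judged by a Z test against updated historical data, so it can be argued that neither 8 nor 7 is the decision rule. This has some force, and step 6 shows that a small shift in the historical count moves the limit. It does not explain the discrepancy, because both sentences start from 26%. It adds a second thing to settle.

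**The summary may only restate target rates.** The power text uses 12% and 60%; 12% of 60 is 7.2 and 60% of 60 is 36. That is a plausible origin, but it is an inference, and the sentence still reads as a requirement.

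**Some tests do give 7.** At one-sided 0.025, 8 cases has p = 0.0342 in the continuity-corrected pooled two-sample Z test and 0.0306 in Fisher's exact test, so 7 is the limit for both. The plan names neither form, and its decision sentence uses 0.05.

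**It is a pilot.** The study describes itself so, and only one outcome is affected. That limits the consequence. The plan nevertheless claims a demonstrated effect at p < 0.05.

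**Stronger readings that a reader might infer.** One is that grade II has the same contradiction, 37 against 36. The documents do not support this: the summary's 36 can be read as an example that meets the limit of 37. Another is that 7 and 36 reflect a deliberate stricter alpha, since an exact test at 0.0125 gives that pair. In the documents that level appears only for the microbiome diversity comparisons, never for efficacy. A third is that a limit of 7 breaks the 0.8-power claim in section 8.2. Power there is 76.2% at a 62% reduction, but the section says only about 62% and elsewhere 60-70%, and 80% is reached at a 63.8% reduction. The claim is too approximate to be contradicted.

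**Conclusion.** The contradiction holds for grade III-IV GVHD and must be resolved. The endpoint sentence, the exact-test table and, with the current historical data, every Z form tried at 0.05 agree that 8 cases is a success; the summary sentence alone disagrees.

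The conflict decides the outcome in roughly one trial in nine to one in seven if the true rate is 10% to 12%, and rarely (0.85%) if telmisartan has no effect. Moving from 8 to 7 costs 10.6, 12.8 and 14.3 percentage points of power at 10%, 11% and 12%. Separately, the 82.2% at 12% does not describe either stated limit.

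These figures assume independent patients, exactly 60 analysed, and P0 = 0.26 treated as known, except in the two-sample tests, which use 46/178. For grade II, the 36 needs only a wording clean-up, but no grade II limit is usable until the counted event is defined.

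**What to change.** Before the data are seen:

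1. Correct the closing summary of section 8.3.1 to 8 or fewer, matching the endpoint sentence and the exact-test table. If 7 is intended, change the endpoint sentence and the table instead, state the test and alpha that give 7, and restate the power as 75.2% / 66.2% / 56.7% at 10% / 11% / 12%.
2. State one test with its form, and one one-sided alpha, for that limit. If the exact test at one-sided 0.025 is kept with a limit of 8, quote 85.8% / 79.0% / 71.0% at 10% / 11% / 12%, and remove the 5%-level powers, so that 71.0% replaces 82.2% at 12%.
3. Say whether the limit is fixed at P0 = 0.26 or recomputed from the updated historical data, and if recomputed, give the formula.
4. For grade II, define the counted event first, then state one limit and mark 36 of 60 as an example or remove it.

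The cost for grade III-IV is wording only, with n unchanged at 60. The stated power at a 12% rate becomes less favourable.
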